10.5 STUDY OVD SUPPLY

The investigational OVD will be obtained from a site consignment that is supplied by the Sponsor following IRB approval for a given site. [REDACTED]

The control OVD will also be obtained from a site consignment that is provided by the Sponsor specifically for use in the study.

10.7 OPERATIVE PROCEDURES

Both the investigational and the control OVDs should be generally used as the investigator would use his/her standard OVD(s) during the cataract removal and lens implantation procedure. [REDACTED]

[figure not shown]

[figure not shown]
A large black rectangular redaction box covers the majority of the page content, starting below the header and ending above the footer. The redaction is composed of several horizontal black bars of varying lengths, creating a stepped effect. The redacted area is approximately 85% of the page's width and 75% of its height.

10.8 POSTOPERATIVE PROCEDURES

Postoperatively, subjects will be examined according to the schedule

10 of 10

ADVERSE EVENTS

Subjects should be assessed at each visit for occurrence of and/or change in status of any adverse events, particularly serious and/or device-related adverse events. [REDACTED]

10.9 EXIT OF SUBJECTS

An Exit Case Report Form will be completed for all subjects, either when they complete the study or if they exit early.

It is the responsibility of the investigator to provide complete follow-up data to JJSV for each subject, and every attempt should be made to gather that complete follow-up data for all subjects enrolled as missing data can have a negative effect on the study results. Patients who would be traveling, relocating or otherwise unavailable for postoperative follow-up visits should not be chosen for this clinical study.

Subjects will be discontinued/early terminated from the study if the subject dies, or if the subject is irretrievably lost for unavoidable reasons such as: subject moved/unable to locate, subject uncooperative/refuses further study participation, subject ill/unable to travel. Documentation of efforts to trace subjects that are lost to follow-up and possible reasons are required. In the event of subject relocation, efforts must be made by the

investigator to secure follow-up information (i.e., slit-lamp findings and general visual acuity, etc.) from the subject's new physician.

A subject will be considered a non-randomized screen failure if he/she does not meet the inclusion/exclusion criteria, if consent is withdrawn prior to randomization or death occurs prior to treatment.

A subject will be considered a randomized screen failure if the subject is randomized but does not undergo surgery or does not receive a study/control OVD for various reasons including: subject does not meet the inclusion/exclusion criteria, the planned implant was aborted due to surgical complications, the subject withdrew consent prior to treatment or the subject died prior to treatment. If a subject receives the study or control OVD in at least one eye, he/she is to be followed according to the protocol.

If a subject is exited early from the study, the investigator will complete an Exit Case Report Form in EDC indicating the reason for study exit. In the event of a lens removal or other serious adverse event, the subject may be exited from the study; however, efforts must be made by the investigator to follow the subject until resolution of the adverse event.

Following study completion or early exit, subjects may be informed about which OVD model they received. Additionally, all study subjects are to be instructed to undergo regular eye examinations at least yearly and also to return to their doctor if any eye complications are experienced in the interim.

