10.4 RANDOMIZATION AND MASKING

A randomization list stratified by investigational sites will be created [REDACTED] [REDACTED] Subjects will be randomly assigned to receive either the Healon EndoCoat PRO or the Healon EndoCoat control in the first operative eye in a 1:1 ratio; subjects will then receive the OVD not used in the first-eye surgery in the fellow eye. Unmasked study personnel at the site will be trained in the randomization process through the EDC system and will randomize subjects as they are enrolled. Randomization will take place after the subject has signed the informed consent document, has met all inclusion and exclusion criteria, and the investigator has documented which eye will be the first to undergo surgery.

As part of the informed consent process, the investigator or delegate will explain to the subject the requirements of a randomized study and the differences between the two OVDs: the Healon EndoCoat PRO investigational OVD and the Healon EndoCoat control OVD.

The subjects, investigators, and the study technicians performing the postoperative exams are to be masked through study completion. [REDACTED]

Unmasked Clinical Research Associates (CRAs) will visit the site to confirm OVD traceability and to monitor Operative visit forms and source documents. All other JJSV study personnel will remain masked through the final study visits.

[figure not shown]

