11.4 CAUSAL RELATIONSHIP

The investigator should always be alert to adverse events that may be related to the study device or the use of the study device (i.e., the procedure specific to the initial application of the device). An attempt should be made in every case to determine the causality of the event. The following definitions are to be used as guidelines in determining the relationship between the event and the study device and/or use of the device.

Definitely related:	If the event is associated with the device and/or the use of the device beyond a reasonable doubt, a causal relationship exists between the adverse event and the device and/or the use of the study device.
Probably related:	There is a reasonable possibility of a causal relationship between the adverse event and the device and/or the use of the study

device and/or the adverse event cannot be reasonably explained by another cause.

Possibly related: The adverse event has not been determined to be related to the device or the use of the device, but no other cause has been identified and the device and/or the use of the study device cannot be ruled out as a possible cause.

Unlikely to be related: The possibility of a potential causal relationship between adverse event and the device and/or the use of the device could exist, but the adverse event can be reasonably explained by another cause.

Not related: There is no possibility of a causal relationship between the adverse event and the device and/or the use of the study device and/or the adverse event can be attributed to another cause.

If an adverse event is believed to be definitely, probably or possibly related to the study device and/or the use of the device, the event will be considered related to the study device and/or the use of the device.

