11.5 ADVERSE EVENT FOLLOW-UP

For every adverse event, appropriate measures should be undertaken to treat and/or monitor the subject until resolution occurs. Obtain and maintain in the subject's files all pertinent medical data relating to the event including the subject's medical records and medical reports and/or judgments from colleagues or outside specialists who assisted in the treatment and follow-up of the subject. The investigator should keep JJSV closely informed as to the outcome of serious and/or device-related adverse events, thereby allowing JJSV to comply with the appropriate regulatory reporting requirements. A Detailed Adverse Event Update CRF should be completed each time the subject returns to the investigator or other specialist(s) for follow-up of serious and/or device-related adverse event until resolution of the event. Any subject who is exited from the study due to a serious and/or device-related adverse event will be followed until the outcome is determined.

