### 1.4 RANDOMIZATION AND MASKING

A randomization list stratified by investigational sites was created by a JJSV biostatistician who is independent and not involved in the study activities. Subjects are randomly assigned to receive either the Healon EndoCoat PRO or the Healon EndoCoat control in the first operative eye in a 1:1 ratio; subjects then receive the OVD not used in the first-eye surgery in the fellow eye. Randomization will take place after the subject has signed the informed consent document, has met all inclusion and exclusion criteria, and the investigator has documented which eye will be the first to undergo surgery.

The subjects, investigators, and the study technicians performing the postoperative exams are to be masked through study completion. To maintain subject/technician-masking through the 3-month study exams, a masking plan will be tailored for each site to detail how OVD assignment information will be concealed from masked technicians. Recommended steps to maintain masking include ensuring that all items pertaining to OVD assignment and records are kept separately from all other study documents and subject medical records until after completion of the final study visit. For example, OVD logs (indicating the OVD model used in each eye) may be kept in the operating room study notebook until completion of the final study visit, at which time they may be placed in the subject medical charts.

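### Protocol 10.9 lets a subject be told the OVD at early exit, when adverse event follow-up may still be open and masking is required through study completion

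*Protocol*

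**What the plan says.** **Masking.** Protocol 10.4, repeated in SAP 1.4, says: "The subjects, investigators, and the study technicians performing the postoperative exams are to be masked through study completion". For sponsor staff other than the unmasked CRAs, 10.4 adds: "All other JJSV study personnel will remain masked through the final study visits". SAP 1.4 describes the aim of the site masking plans as follows: "To maintain subject/technician-masking through the 3-month study exams, a masking plan will be tailored for each site".

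**Disclosure.** Protocol 10.9 says: "Following study completion or early exit, subjects may be informed about which OVD model they received". The visible text attaches no condition about adverse events that are still open.

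**Follow-up after exit.** When a subject leaves after a lens removal or another serious adverse event, 10.9 says that "efforts must be made by the investigator to follow the subject until resolution of the adverse event". Protocol 11.5 says: "Any subject who is exited from the study due to a serious and/or device-related adverse event will be followed until the outcome is determined". It also asks for an update form at each return visit for a serious and/or device-related event until that event resolves.

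**Causality.** Protocol 11.4 says: "An attempt should be made in every case to determine the causality of the event". It sets no time by which this must be done.

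**Logs.** SAP 1.4 gives, as an example of a recommended step, that OVD logs may stay in the operating-room notebook "until completion of the final study visit, at which time they may be placed in the subject medical charts".

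**The concern.** Early exit happens to one subject at a time, while the trial is still running. Subjects who leave because of a serious or device-related event are also the ones whose data collection explicitly continues after exit. If such a subject is told the OVD, later symptom reports, the recorded outcome and any further judgement of relatedness are no longer protected by masking.

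This is a subject- and evaluator-masked safety and effectiveness comparison of two closely similar products. Unmasked follow-up of its most serious events would weaken the part of the safety record that depends most on judgement. If OVD logs entered charts while events were open, they would provide a second route to the same knowledge.

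**Working it through.** No figure in the plan bears on this point, and the sample size section is redacted, so there is nothing to recompute. The check compares the rules with one another.

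1. **Is early exit the same as study completion?** No. Protocol 10.9 names them as alternatives in the disclosure sentence. It also has the Exit form completed either when a subject completes the study or on leaving early.

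2. **Does the conflict depend on what study completion means?** The term is not defined.
   - If it refers to the trial, a subject told at early exit is unmasked before the trial ends.
   - If it refers to the subject, an early leaver never reaches it, so the masking rule in 10.4 gives no end point for that subject, while 10.9 permits disclosure.
   - On both readings 10.9 allows disclosure at a time that 10.4 and SAP 1.4 do not provide for.

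3. **Are data still being recorded then?** Yes, for some subjects. Protocol 10.9 and 11.5 continue follow-up after an exit for a serious and/or device-related event until resolution or outcome, with update forms.

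4. **Is relatedness still open then?** Possibly. Protocol 11.4 wants causality determined in every case but sets no deadline. No visible text requires it to be settled before disclosure, and none says it is revisited after exit.

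5. **How much does one disclosure reveal?** Under 10.4 the fellow eye receives whichever OVD the first eye did not. Where both eyes have been treated, learning one assignment gives both.

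6. **Who becomes unmasked?** Protocol 10.9 speaks only of the subject. The investigator, who judges causality, could then hear it from the subject during follow-up.

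7. **What of completers?** On a subject-level reading, telling a completer is consistent with 10.4, but an event may still be open. Note 3 in Protocol 11.1 treats low-grade uveitis or iritis as serious if it lasts beyond 3 months. That judgement can fall after the 3-month visit, so the remedy should cover completers too.

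8. **Are the primary tests touched?** Hardly. A completer's IOP and ECC data are already collected at disclosure, and an early leaver normally contributes no further primary endpoint data.

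**The case against.** The strongest reply is that this is a small gap in wording. The exit section uses completion in a per-subject sense, and the SAP aims at masking through the 3-month exams. On that view masking ends when a subject's own participation ends, and 10.9 merely says so. Safeguards also exist. Protocol 11.3 requires serious events to reach the sponsor within 48 hours of detection, with a completed detailed form, so an initial assessment will often precede disclosure. The Medical Monitor reviews these events, and sponsor personnel other than unmasked CRAs stay masked through the final visits. Protocol 14.1 restricts OVD identification in source records to unmasked staff. Text after the masking sentence in 10.4 is redacted and may add detail.

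Much of this stands, and it limits the point. It does not remove it. Early reporting secures an initial assessment, but the outcome is by definition recorded later, and nothing visible prevents a later change in relatedness. The subject's own reports are not protected by masking at the sponsor.

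The reply is strongest on the logs. A reader might infer that SAP 1.4 contradicts 10.4. It does so only if study completion refers to the trial. On the subject-level reading the two agree, and the sentence is only an example within site plans that are not shown. The logs therefore belong in the fix as an alignment item and are not a second contradiction.

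**Conclusion.** The point holds in a limited form. Protocol 10.9 permits disclosure at early exit, which the masking rule in 10.4 and SAP 1.4 does not accommodate, and some of these subjects remain under adverse event follow-up. The exposure is in the recorded outcome and possibly the relatedness of serious and/or device-related events. The two non-inferiority tests are not materially affected. It is a cheap improvement and does not threaten the main conclusions.

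The verdict assumes that disclosure at exit is actually used and that no redacted text restricts it.

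Four stronger readings are not supported:

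- **That the investigator and the chart are necessarily unmasked, or that causality is re-judged after exit.** Both are possible, but neither is stated.
- **That the number affected can be read from the enrolment figures.** The gap between 195 enrolled and about 114 evaluable is 195 − 114 = 81 subjects, or 81/195 = 41.5%. This can include screen failures, subjects with one treated eye and completers who are not evaluable. Some early leavers have died or cannot be traced. The number who exit with an open event is not given.
- **That 10.9 circumvents the unmasking procedure in 15.3.** That procedure governs release of the code at the Medical Monitor's request for safety, which is a different situation.
- **That knowledge of past assignments could influence which eye is named first.** This would need blocked assignment and masked staff who learn and use earlier assignments. Block details are not visible.

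**What to change.** **Protocol 10.9.** Replace the disclosure sentence with one stating that subjects may be told which OVD each eye received only after database lock. If that wait is thought too long, the minimum is to allow disclosure only once every open adverse event of that subject has a recorded outcome and a dated causality assessment. Leave the safety unmasking route in 15.3 unchanged.

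**SAP 1.4.** State that OVD logs remain in the operating-room binder until the same point. This fits Protocol 15.2, which already keeps the site log there.

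**Protocol 14.1.** Reconcile the log rule with this section, which requires OVD serial number identification in the source records and limits its review to unmasked staff. State where that entry is held until release.

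**Terms.** Say in 10.4 whether study completion and final study visit refer to the subject or to the trial.

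**Cost.** A sentence or two in each of these places, with no change to sample size, visits or analysis. The downside is that subjects wait longer to learn their OVD. The minimum option shortens that wait but requires the site to check for open events before each disclosure.

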10.10 UNSCHEDULED VISITS

During the study period, if a non-protocol-required visit is done for the purpose of medically-indicated follow-up for either study eye, data from this visit should be submitted using the Unscheduled Visit CRF. The need for unscheduled visits is at the investigator's discretion. Specific examinations to be performed at unscheduled visits are also at the discretion of the investigator (based on the reason for the unscheduled visit), and data are to be recorded in the appropriate section of the case report form.

Data to be collected may include:

- Uncorrected and best corrected distance visual acuity
- Manifest refraction
- Intraocular pressure
- Slit-lamp examination for medical and/or lens findings
- Dilated fundus exam
- Adverse events
- Ocular Medications

10.11 PROTOCOL DEVIATIONS

Any departure from the protocol procedures represents a protocol deviation. Protocol deviations may be subject-based (e.g., inclusion/exclusion criteria, informed consent deviation, etc.) or procedural-based (e.g., out-of-interval visits, non-compliance with testing procedures, etc.). All protocol deviations will be documented, and corrective actions will be implemented as appropriate. Any deviation made to protect the life or physical well-being of a subject in an emergency as well as any use of the investigational device without obtaining informed consent must be reported to JJSV within 5 working days. Protocol deviations will be monitored by JJSV, and if the non-compliance is persistent or egregious, JJSV may take action, including but not limited to termination of the investigator's participation in the study. The investigator is also responsible for informing the reviewing IRB of instances of protocol non-compliance in accordance with the IRB requirements. JJSV cannot grant permission to use waiver from the study protocol.

11. ADVERSE EVENTS AND PRODUCT COMPLAINTS

11.1 ADVERSE EVENT DEFINITIONS

Adverse Event (AE)

An adverse event is defined (following ISO 14155) as any untoward medical occurrence, unintended disease or injury, or untoward clinical signs (including abnormal laboratory findings) in subjects, users or other persons, whether or not related to the study device.

Serious Adverse Event (SAE)

An adverse event is considered serious (following ISO 14155) if it is an untoward occurrence which may or may not be related to use of the study device that

- is sight- or life-threatening,
- results in death,
- requires inpatient hospitalization or prolongation of hospitalization (a planned hospitalization for a pre-existing condition without a serious deterioration in health is not considered a serious adverse event),
- results in permanent impairment of a body structure or body function including chronic diseases,
- necessitates medical or surgical intervention to prevent permanent impairment to a body structure or function, or
- results in fetal distress, fetal death or a congenital abnormality or birth defect including physical or mental impairment

Device-Related Adverse Event/Adverse Device Effect (ADE)

A device-related adverse event is defined as any adverse even that is believed to be definitely, probably or possibly related to the study device (following the guidelines in Section 11.4, Causal Relationship). A device-related event is also considered an adverse

device effect (ADE; following ISO 14155) resulting from the use of the study device that may result from user error, insufficiencies or inadequacies in the instructions for use, deployment, implantation, installation, operation of any malfunction of the device.

Study-Specific Serious Anticipated Adverse Events

The following is a list including, but not limited to, ocular adverse events that are anticipated and must be reported to JJSV for this study. Any events that are unlikely but anticipated (i.e., endophthalmitis) will be reported to the FDA and other appropriate regulatory agencies.

- Endophthalmitis/Intraocular infection
- Hypopyon
- Hyphema
- IOL dislocation
- Cystoid macular edema
- Pupillary block
- Retinal detachment/tear
- Persistent corneal edema
- Persistent iritis
- Raised IOP requiring treatment (i.e., IOP \geq 30 mmHg)
- Visual symptoms requiring secondary surgical intervention (e.g., lens removal)
- Tilt and decentration requiring secondary surgical intervention (e.g., repositioning)
- Residual refractive error resulting in a secondary surgical intervention
- Retained lens material resulting in secondary surgical intervention

NOTE 1: Suture removal, planned blepharoplasty and Nd:YAG capsulotomy (for PCO) are not considered adverse events for this study.

NOTE 2: Corneal edema and iritis will only be considered serious if sight-threatening at the time of occurrence. Treatment merely to hasten the resolution of such conditions (and not intended to prevent permanent damage to the eye) will not be reported as serious adverse events.

NOTE 3: Corneal edema, and chronic anterior uveitis/iritis will be considered serious if corneal edema results in BCDVA of 20/40 or worse at 1 month or later; and Grade 1+ uveitis/iritis persists longer than 3 months.

Unanticipated Adverse Device Effect (UADE)/Unanticipated Serious Adverse Device Effect (USADE)

Any UADE (USA 21CFR 812.3(s)) or USADE (ISO 14155) is defined as any serious adverse effect on health or safety or any life-threatening problem or death caused by, or associated with, a device, if that effect, problem, or death was not previously identified in nature, severity, or degree of incidence in the investigational plan (i.e., this protocol), application (including a supplementary plan or application), or risk assessment, or any

other unanticipated serious problem associated with a device that relates to the rights, safety, or welfare of subjects.

Serious Health Threat

A serious health threat (following ISO 14155) is a signal from any adverse event or device deficiency that indicates an imminent risk of death or a serious deterioration in the health in subjects, users or other persons, and that requires prompt remedial action for other subject, users or other persons. This would include events that are of significant and unexpected nature such that they become alarming as a potential serious health hazard or possibility of multiple deaths occurring at short intervals.

